11.1.1 Safety analysis set

The Safety Analysis Set will consist of all patients who received at least one dose of Durvalumab. Analyses of safety data will be performed on this analysis set.

11.1.2 Efficacy analysis set

Since this trial is a pilot study and patients are not being randomized, the "efficacy" analysis set used for this study will be equivalent to a "per protocol" analysis set rather than a traditional intent-to-treat analysis set. With this in mind, the efficacy analysis set will include all patients who received at least two doses of Durvalumab and had CT scans or MRIs and blood, saliva and tissue collected before and after treatment. All analyses of primary and secondary outcomes (except for safety) will be performed using this analysis set.

11.2 Methods of statistical analyses

11.2.1 Safety Analyses

Analysis of safety endpoint(s)

All safety endpoints (adverse events (AEs)) described above will be documented. AEs will be coded using the MedDRA dictionary to their organ class by preferred term. Coded AEs will be displayed by frequency, severity, and relationship to treatment (Durvalumab) in the safety population. In addition, summary tables will be generated for the following situations: 1. fatigue, diarrhea, nausea and skin rash; 2. Immune-mediated reactions of any grade; 3. other adverse events graded as 3 or more by CTCAE Version 4.03; 4) Durvalumab dose reductions; 5) discontinuations of treatment with Durvalumab, with specification of reason for discontinuation; and 6) changes in the surgical treatment schedule with specification of reason will be provided using descriptive statistics.

Descriptive statistics will be gathered on additional measurements that will be collected. These include displays of mean, median, standard deviations and ranges for continuous measures and counts and percentages for categorical measures.

11.2.2 Efficacy Analyses

As stated above, there are several primary efficacy measures for this protocol. In addition, this is not a randomized clinical trial, thus there is not one primary efficacy analysis, rather there are a series of primary analyses proposed to be performed examining each of the primary efficacy measures described above.

Analysis of immunogenicity

- Peripheral blood mononuclear cell interferon-γ production in vitro (ELISA) in response to commercially available peptide pools corresponding to HPV, p53, Mage-A3, Her2/neu, and survivin will be compared between patients who are HPV+ and HPV- using 2 sample t-tests. These measures will be compared in several ways. First, baseline, pre-treatment levels will be examined using descriptive statistics (n, mean, standard deviations, range). These measures will be examined overall and by HPV (+/-) groups. For each measure, and time point, 95% confidence intervals will be estimated. Next, two sample t-tests will be performed to compare levels of the measures at baseline. Next, measures taken post-treatment will be examined in a similar manner (descriptive statistics and 2-sample t-tests). Finally, comparisons between HPV+ and HPV- groups will be made by comparing the changes (pre-treatment to posttreatment) between groups using 2-sample t-tests.
- 2) Concentration of certain immune effector and regulatory cells will be assessed in blood (CD4+, CD8+, CD4+FoxP3+ Treg, and CD45RO+CD4+ memory T cells; CD3-CD56+ NK cells, and CD14-HLA-DR-CD15+ MDSC) pre- and post- treatment. Descriptive statistics, confidence intervals will be calculated and 2-sample t-tests will be performed as described above for the interferon- γ analyses.
- 3) Tumor-infiltrating immune-regulator and effector cells will be quantified (0 to 3+) using standing immunofluorescence techniques. Counts and percents will be calculated for these measures overall and by HPV (+/-) groups pre- and post-treatment. Fisher exact tests will be used to compare groups at pre- and post- treatment. Stuart-Maxwell tests (generalizations of the McNemar's Test) will be used to examine changes between groups (HPV +/-) from pre- to post- treatment.
- 4) Levels of immune-regulatory miRs assessed in blood, saliva and tumor tissue will be assessed pre- and post- treatments. Descriptive statistics, confidence intervals will be calculated and 2-sample t-tests will be performed as described above for the interferon- γ analyses. In addition, correlations between the different methods will be examined (i.e., correlation between saliva and blood measures, saliva and tumor measures, and blood and tumor measures).

Secondary endpoint analyses

Measures of tumor volume will be assessed using RECIST 1.1 criteria. These tumor volumes will be compared between groups (HPV +/-) pre- and post- treatment. Descriptive statistics, confidence intervals will be calculated and 2-sample t-tests will be performed as described above for the interferon- γ analyses.

SUV activity as measured by PET scans will also be compared between groups at each time point and descriptive statistics, confidence intervals will be calculated and 2-sample t-tests will be performed as described above for the interferon- γ analyses.

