1. INTRODUCTION

1.1 Disease Background

Oropharynx cancer (OPC), a subset of squamous cell carcinoma of the head and neck (SCCHN), is often associated with human papillomavirus (HPV) infection. It has been proposed that the favorable prognosis observed in HPV+ vs. HPV- OPC may be due to immune responses directed against viral antigens. Tumor-infiltrating CD4+ and CD8+ T cells in OPC are associated with a favorable prognosis. HPV-specific T cells can also be grown from tumor biopsies, suggesting that at least some of the infiltrating T cells are HPV-specific. Immune responses to several tumor-associated determinants have also been implicated in HPV+ and HPV-HNSCC, including p53, Mage-A3, Her2/neu, and survivin.

Immune responses directed against tumors are one of the body's natural defenses against the growth and proliferation of cancer cells. However, over time and under pressure from immune attack, cancers develop strategies to evade immune-mediated killing allowing them to develop unchecked. One such mechanism involves upregulation of surface proteins that deliver inhibitory signals to cytotoxic T cells. Programmed cell death ligand 1 (PD-L1) is one such protein, and is upregulated in a broad range of cancers with a high frequency, with up to 88% expression in some tumor types. In a number of these cancers, including lung (Mu et al, 2011), renal (Thompson et al, 2005; Thompson et al, 2006; Krambeck et al, 2007), pancreatic (Nomi et al, 2007; Loos et al, 2008; Wang et al, 2010), ovarian cancer (Hamanishi et al, 2007), and hematologic malignancies (Andorsky et al, 2011; Brusa et al, 2013) tumor cell expression of PD-L1 is associated with reduced survival and an unfavorable prognosis.

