1.3 Research hypothesis

Based on preliminary data showing that the presence of HPV antigens is contributing to increased anti-tumor T cell activity in patients with SCCHN, we hypothesize that immunotherapy with PD-L1 antibody will lead to more intense and efficient specific immune activation against the SCCHN tumor in HPV + patients compared with HPV - patients. We also hypothesize that an extensive analysis of the blood and saliva might lead to identification of markers predictive of a more efficient response to PD-L1 inhibition. Lastly we would like to test the ability of PET scan to detect an increased immune response. One can hypothesize that a corresponding increase in the immune response with an increase in the number of infiltrative activated immune cells could be associated with an increase in metabolic activity measured by PET SUV. Similarly, an effective anti-tumor activity of the

activated immune response could lead to decreased metabolic activity. We are interested in evaluating the dynamic in the metabolic activity early in the treatment and to attempt to detect potential consistency that could be used in future therapeutic paradigms.

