8.3.1 Immunogenicity sampling and evaluation methods

Blood and saliva will be collected pre- and post-treatment with Durvalumab.

Blood (20 ml) will be drawn into EDTA tubes. Samples will be labelled and transported at rrom temperature within one hour to [name] laboratory in Hanes building 5th floor. Peripheral blood mononuclear cells (PBMC) are isolated from whole blood by density gradient centrifugation using Lymphocyte Separation Medium (Mediatech) and Leucosep tubes (Greiner Bio-one). Whole blood is centrifuged at 410 × g for 10 minutes and the plasma layer is collected, centrifuged for 10 minutes at 885 × g, and the supernatant frozen at -80° C for subsequent experiments. The whole blood is diluted 1:1 with RPMI (Mediatech) and the PMBCs isolated per manufacturer's guidelines. Cells at the interface are harvested and washed once with RPMI, and red blood cells are lysed with ammonium chloride lysis buffer. Cells are washed, counted, and immediately used fresh for staining and flow cytometry analysis, or 10 million PBMCs are frozen per milliliter of freezing solution (10% DMSO 10% FBS-supplemented RPMI) per NUNC cryovial. PBMCs are frozen in a Nalgene Cryo 1°C freezing container per manufacturer's instructions and stored in liquid nitrogen thereafter.

PBMC and plasma will be used for the following assays:

1. Examine the effects of Durvalumab on systemic immune response to HPV and tumor associated antigens. Peripheral blood mononuclear cell interferon- γ production in vitro in response to commercially available peptide pools corresponding to HPV, p53, Mage-A3, Her2/neu, and survivin will be determined.

PBMC that have been separated by gradient centrifugation and cryopreserved are thawed at 37 °C, diluted in 5 ml RPMI, and incubated at 37 °C for 1 hour. Cells are then pelleted at 200g, resuspended in complete medium, counted with trypan blue, and suspended at 4x106/ml and plated in 100 µl in 96 well conical wells. PBMC are then cultured with 20 µg/ml of WT-1, p53, Her2/neu, Mage-A3, telomerase, and survivin peptide mixtures ProMix Peptide Pools (Proimmune Inc.). As a control PBMC are also stimulated with anti-CD3 plus anti-CD28 antibody (BD Pharmingen). After 3 days, culture supernatants are collected and assayed using commercially available ELISA kits according to the recommendation of the manufacturer. Results are expressed as a concentration.

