9.1.2. FDG-PET Scan

PET scan will be obtained before and after treatment whenever approved by Medical Insurance or funded. The initial PET scan should be obtained as close to the treatment start date as possible, with a maximum window period of 28 days. Similar technique and dosing of the 18-Fluoro-deoxyglucose should be targeted. Percentage change in SUV activity between the initial scan (obtained before treatment with Durvalumab) and follow up scan (obtained after treatment with Durvalumab and before surgery) will be reported for each targeted lesions identified on CT scan based on RECIST 1.1.

Little is known about the effect of short course of treatment with Durvalumab on metabolic activity in the tumor. While this can decrease due to inhibition of tumor growth, it is also possible that the metabolic activity measured at primary tumor site and lymph nodes to be increased initially due to increase in number and activity of inflammatory and immune effective cells.

Changes in SUV will be reported to changes in measurements by CT scan or MRI for each lesion.

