11. STATISTICAL METHODS AND SAMPLE SIZE DETERMINATION

11.1 Description of analysis sets

Primary Objectives

The primary objectives of this pilot study are to investigate the effect of Durvalumab on local and systemic immune activation and compare the results in HPV positive and HPV negative patients with oral cavity and oropharynx HNSCC. Tumor tissue, blood and saliva will be collected before and after treatment with Durvalumab and will be analyzed for systemic immune response to HPV and tumor associated antigens and impact on immune regulatory mechanisms in tumor and blood. Levels of immune-regulatory miR in plasma and saliva will be correlated with other parameters of the local and systemic immune response in order to identify possible predictors of response. Results will be compared between HPV positive and negative patients to identify a possible differential effect of treatment with Durvalumab. Level of local immune response in the primary tumor and in the regional lymph nodes will be compared whenever possible.
Secondary Objectives

- A. Investigate the effect of the treatment with Durvalumab on measures of tumor volume (from the CT scan) and tumor activity (from the PET scan).
- B. Evaluate the safety of a short induction treatment with Durvalumab.

Primary Endpoints:

Since this is a pilot study and does not have a specific primary efficacy analysis, there are several primary endpoints (rather than a single primary efficacy endpoint) that will be collected. These can be described in three broad categories within the area of local and systemic immune activation. The categories are effects of Durvalumab on 1) systemic immune response to HPV and tumor associated antigens; 2) immune regulatory mechanisms; and 3) immune-regulatory miR responses as measured in plasma, saliva or tumor. Each of these categories has several endpoints that will now be described.

- 1. Systemic immune response to HPV and tumor associated antigens:
 - a. Peripheral blood mononuclear cell interferon-γ production in vitro (ELISA) in response to commercially available peptide pools corresponding to HPV, p53, Mage-A3, Her2/neu, and survivin will be determined.
- 2. Immune regulatory mechanisms.
 - a. The following immune effector and regulatory responses will be assessed in blood using standard flow cytometric techniques: CD4+, CD8+, CD4+FoxP3+ Treg, and CD45RO+CD4+ memory T cells; CD3-CD56+ NK cells, and CD14-HLA-DR-CD15+ MDSC.

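### Does leaving the scale of interferon-gamma change unstated make the HPV+ versus HPV- comparison unsafe?

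*Combined protocol and SAP*

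**What the plan says.** The interferon-gamma analysis is in section 11.2.2, item 1. It calls for descriptive statistics and 95% confidence intervals overall and by HPV group, and then "two sample t-tests will be performed to compare levels of the measures at baseline". Post-treatment levels are handled the same way. Last, "comparisons between HPV+ and HPV- groups will be made by comparing the changes (pre-treatment to posttreatment) between groups using 2-sample t-tests". Items 2 and 4 and the secondary endpoints refer back to this method.

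Other text bears on the scale:

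- Section 8.3.1, on the ELISA: "Results are expressed as a concentration".
- Section 11.3 and the synopsis treat a significant change as the measure moving up or down by more than 0.72 SD.
- Section 9.1.2, on PET, reports "Percentage change in SUV activity between the initial scan" and the follow-up scan for each target lesion. Section 9.1.1 does likewise for CT or MRI size. In section 11.2.2, "SUV activity as measured by PET scans will also be compared between groups at each time point".

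Section 11.1 gives the purpose: "Results will be compared between HPV positive and negative patients to identify a possible differential effect of treatment with Durvalumab".

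**The concern.** The groups are defined by HPV status, not by randomisation, so their starting levels may differ. Section 1.3 gives a reason to expect this: "the presence of HPV antigens is contributing to increased anti-tumor T cell activity in patients with SCCHN". When starting levels differ, an equal effect on one scale is unequal on the other. An equal fold-rise gives a larger raw rise in the group that starts higher. An equal raw rise gives a smaller ratio in that group.

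Item 1 fixes no scale for change and does not say how a baseline difference should affect the reading of the change test. A reader could therefore take a difference in starting level for an HPV-specific drug effect, with its direction set by the scale used. This contrast serves the primary objective, so a misread signal could pass into the planning of later studies. The remedy in view is to test both scales and to claim a differential effect only when both are significant in the same direction.

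**Working it through.** **The plan's own figures.** Section 11.3 gives 10 patients per group.

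- Confidence interval half-width: t(0.975, 9)/√10 = 2.262/3.162 = 0.715 SD, the stated 0.72.
- Power for 1.3 SD, two-sided alpha 0.05, 18 degrees of freedom, noncentrality 1.3 × √(10/2) = 2.907: 78.5%, close to the stated 80%.

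Both are in SD units and hold for whichever scale is analysed. The sample size does not depend on the answer.

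**The arithmetic of the concern.** Take assumed baselines of 200 (HPV+) and 100 (HPV-).

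- Both rise 1.5-fold: raw changes are +100 and +50, while both ratios are 1.5.
- Both rise by 50: raw changes are equal, while the ratios are 250/200 = 1.25 (log change 0.22) and 150/100 = 1.50 (log change 0.41).

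So the mechanism is real whenever baselines differ.

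**How often it reaches significance.** The documents give no SD, pre/post correlation, baseline gap or detection limit, so all of these are assumed: log-normal pairs, 10 per group, log correlation 0.7, pooled two-sample t-test, two-sided 0.05, 40,000 simulated trials per cell. The drug effect is equal in both groups, so every rejection is false.

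| Baseline gap | Log-SD | Raw test, both double | Raw test, both triple | Log-ratio test, equal additive rise of one HPV- median |
|---|---|---|---|---|
| 2-fold | 0.5 | 40% | 59% | 39% |
| 2-fold | 1.0 | 8% | 12% | 13% |
| 2-fold | 1.5 | 3% | 4% | 9% |
| 3-fold | 0.5 | 73% | 92% | 66% |
| 3-fold | 1.0 | 13% | 24% | 23% |
| 3-fold | 1.5 | 4% | 7% | 13% |

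Raw-test rejections nearly all favour HPV+, and log-ratio rejections nearly all favour HPV-. With equal baselines neither test is inflated. Smaller effects weaken the raw-scale result: at a 2-fold gap, equal 1.25-fold and 1.5-fold rises give about 10% and 20% at log-SD 0.5, 4% and 5% at 1.0, and 2.5% and 3% at 1.5. The raw test thus runs from below its nominal 5% to 92%, and nothing in the documents says where this assay lies.

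**What the both-scales rule would do.** Without a detection floor, its false rejection was at most 2.7% (equal fold-rise), 2.8% (equal additive rise) and 3.3% (no rise) over 180 cells. The costs are these:

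- True proportional HPV+ advantage of 1.3 SD of log change, gap 1- to 3-fold: power 64-78%, 46-67% and 29-42% at log-SD 0.5, 1.0 and 1.5, against 78-79% for the log test alone.
- True additive advantage of 1.3 SD of raw change when both groups also rise by the HPV- median: 1-32%, 24-51% and 70-80% at the same log-SDs.
- Detection floor, 3-fold gap, both groups doubling, log-SD 0.5: false agreement in 5%, 17% and 57% of trials when 20%, 50% and 80% of HPV- baselines sit at the floor.

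**Which scale the text implies.** The ELISA result is a concentration, item 1 summarises it by means and SDs with no transformation, and section 11.3 speaks of the measure itself rising or falling. Together these point to post minus pre. The PET text does not overturn that: the percentage there is a per-lesion report, and section 11.2.2 compares SUV at each time point. Neither redefines change for interferon-gamma.

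**The case for a change.** The strongest reply is that settling on the raw difference does not remove the problem. It is the scale on which an equal fold-rise favours HPV+, which is the direction of the trial's own hypothesis. The contrast belongs to the primary objective, and a line of text costs nothing. If the scale were chosen after the data from 10 against 10 patients were seen, the direction of an apparent effect would be open to choice.

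Much of this stands. Item 1 names no scale, the arithmetic is right, and the simulated rates were reproduced on rerunning. Three things limit it.

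- The trigger is not shown for this assay. Section 1.3 speaks of anti-tumour T cell activity in general, whereas the endpoint is cytokine release by blood cells. A higher HPV+ baseline is plausible mainly for the HPV pool, one of five, since section 1.1 says: "Immune responses to several tumor-associated determinants have also been implicated in HPV+ and HPV-HNSCC, including p53, Mage-A3, Her2/neu, and survivin".
- A larger raw rise in HPV+ patients is an error only if an equal effect means an equal fold-rise. The documents take no position on that, and neither scale is safe under both meanings.
- The plan shows the reader what is needed. Means, SDs, ranges and intervals are given before and after treatment in each group, and baselines are tested. A gap would be visible and the group means could be compared either way.

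**Conclusion.** The concern does not call for a change. The undefined word is a gap that an analyst would fill with the post-minus-pre concentration, and the rest of the text supports that reading. The possible distortion ranges from none (equal baselines, or wide spread with a modest rise) to a false-rejection rate of 92% (3-fold gap, log-SD 0.5, both groups tripling). That range rests wholly on assumed gaps, SDs, correlation and effect sizes. The documents do not show that the natural reading gives a wrong result.

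Sections 11.1 and 11.3 describe a pilot with no single primary efficacy analysis, meant to give preliminary descriptive data. No go/no-go decision hangs on this test, so the most that could follow is a misread preliminary signal. The both-scales rule is a disputable trade: it gives up much power for true effects and offers no protection at a detection floor, a natural worry for the HPV pool in HPV- patients.

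An analyst may, as a courtesy to readers, state that change is post minus pre, and show the log2(post/pre) comparison with its 95% interval and the number of values below detection by group as a sensitivity analysis, noting where the scales disagree. That is optional reporting detail.

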Tumor (primary tumor and involved lymph node) will be assayed using standing immunofluorescence techniques for PD-1+CD4+, PD 1+CD8+, PD-1L+, and Foxp3+CD4+ tumor-infiltrating cells. The results will be quantified (0 to 3+).

Immunohistochemical staining will be carried out on 4µm-thick sections utilizing an Autostainer Plus (Dako - Agilent Technologies) with appropriate positive and negative controls. Sections are baked for 60 minutes at 60 °C in a dehydration oven and heat-induced epitope retrieved in the PT link (Dako – Agilent technologies) using EnVision FLEX target retrieval solution for 20 minutes at 97 °C then cooled to room temperature in TBST Wash buffer for 5 minutes. Slides are incubated with the diluted antibodies. Antibody detection will utilize the Envision FLEX kit (K8023) with a DAB chromagen for visualization according to the manufacturer's instructions (Dako – Agilent technologies). Slides are then counterstained with hematoxylin. The percentage of tumor which have an infiltrate of lymphocytes or macrophages will be estimated and the average number of positive immune cells per high power field (HPF) in a minimum of 4 representative HPF areas will be determined utilizing a semi-quantitative four tiered scale used for scoring lymphocytes (0= no lymphocytes, 1= 1-10/HPF, 2= 11-50/HPF and 3= >50/HPF) and macrophages (0= no macrophages, 1= 1-50/HPF, 2= 50-100/HPF and 3=>100/HPF). Lymphocyte and macrophage infiltrate scores are obtained by multiplying these scores to attain a score from 0-300.

miRNA will be quantified in tumor tissue and involved lymph node using PCR-based techniques (as described in 8.3.1).

Remaining tissue samples will be retained for future research after the study report has been finalized if agreed by patients in the ICF. Otherwise it will be disposed.

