 - b. Tumor (primary tumor and regional involved lymph nodes) will be collected before treatment and at the time of surgery, after treatment. PD-1+CD4+, PD 1+CD8+, PD-1L+, and Foxp3+CD4+ tumor-infiltrating cells will be quantified (0 to 3+) using standing immunofluorescence techniques.
- 3. Immune-regulatory miR response.
 - a. Levels of immune-regulatory miRs in blood, saliva and tumor (primary and regional involved lymph nodes) will be quantified using PCR-based techniques.

Secondary Endpoints

There are two types of secondary endpoints.

The first consist of measures of tumor volume (via CT scan) or metabolic activity (via PET scan).

The second are measures of clinical toxicities that may occur during the trial.

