11.3 Determination of sample size

The goal for this pilot study is to get preliminary descriptive data for a series of measures taken using blood, saliva and tumor tissue pre- and post- immunotherapy. With a sample size of 10 patients in each group (i.e. 10 with HPV+ and 10 HPV-) a 95% confidence interval for each group will have confidence limits $\pm - 0.72$ standard deviations. In addition, the change in each measure (pre- versus post- therapy) can be used to estimate 95% confidence intervals to determine whether there are any significant changes from baseline (i.e., the measure increased (or decreased) by more than 0.72 standard deviations).

Furthermore, to compare groups (HPV+ versus HPV-), there is 80% power to detect a difference in measures equal to 1.3 standard deviations of the measure of interest using a 2-sample t-test with alpha=0.05.

The patients who are discontinued from the study treatment and/or from the study will be replaced.

It is anticipated that an accrual rate of 12 patients per year is reasonable and thus the goal of 20 evaluable patients should be achieved within approximately 18 months. Additional 6 mo might be needed for accruing replacement patients for the patients unable to complete study treatment or required investigations.

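### Fisher exact tests ignore the order of the 0 to 3+ tumor-infiltrate score, so the pre- and post-treatment HPV contrasts on primary endpoint 2b are valid but less powerful than a rank test, and the only stated power figure does not apply to them

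*Combined protocol and SAP*

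**What the plan says.** Section 11.1 lists, as primary endpoint 2b, four types of tumor-infiltrating cell. It states that "tumor-infiltrating cells will be quantified (0 to 3+) using standing immunofluorescence techniques". Section 8.3.4 repeats that scale and, in its paragraph on immunohistochemical staining, defines a four-tier lymphocyte scale by rising cell count: "0= no lymphocytes, 1= 1-10/HPF, 2= 11-50/HPF and 3= >50/HPF".

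Section 11.2.2 item 3 plans counts and percentages overall and by HPV group. For the group comparisons it says "Fisher exact tests will be used to compare groups at pre- and post- treatment". Changes from pre- to post-treatment go to Stuart-Maxwell tests, which this point does not concern. No rank, trend or other ordinal test is planned for this endpoint.

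Section 11.3 describes the goal as "preliminary descriptive data for a series of measures taken using blood, saliva and tumor tissue pre- and post- immunotherapy". With 10 patients per group, it gives one power figure: "there is 80% power to detect a difference in measures equal to 1.3 standard deviations of the measure of interest". The test named for that figure is the two-sample t-test, at the 0.05 level. The synopsis says the same.

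**The concern.** The score is ordered, but the test is not. On a 2 x 4 table, Fisher's exact test responds to any departure from equal distributions. That includes patterns in which, say, levels 0 and 2+ are common in one group and 1+ and 3+ in the other. No stated hypothesis predicts such a pattern. Sections 1.3 and 1.5.3 speak of more intense immune activation and more immune effector cells in HPV+ disease, which is a shift along the scale. Some of the scored cells are regulatory and might shift the other way, but a two-sided rank test covers a shift in either direction.

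Local immune activation is part of the primary objective, and each group has only 10 patients. Power lost through the choice of test cannot easily be recovered. A reader of section 11.3 also finds one power figure and nothing to say that it does not describe this endpoint.

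**Working it through.** **Inputs from the documents.** 10 HPV+ and 10 HPV-, difference 1.3 SD, alpha 0.05, two-sample t-test (section 11.3); four ordered levels (section 11.1, endpoint 2b); Fisher exact test at each time point (section 11.2.2 item 3). Sidedness is not stated. Two-sided is assumed because it comes closest to the stated figure (a one-sided test would give 87.5%).

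**Step 1: the plan's own figure.** The noncentrality is 1.3 x sqrt(10 x 10/20) = 1.3 x sqrt(5) = 2.907 on 18 df, and the two-sided critical value is 2.101. The noncentral t gives power 78.5%. Exactly 80% needs 1.325 SD. The stated 80% is therefore reproduced to within 2 points, for a t-test.

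**Step 2: why order is lost.** Let t_j be the total in level j and a_j the HPV+ count in that level. Under the null, P(table) = [product over j of C(t_j, a_j)] / C(20, 10). Fisher's p-value sums this over all tables no more probable than the one observed. The product does not depend on the order in which the levels are taken, so permuting the columns leaves p unchanged.

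**Step 3: power on a four-level score.** The documents give no score distribution, so one is assumed: a latent normal with SD 1, mean 0 in the lower group and 1.3 in the higher, cut at c1 < c2 < c3. The level probabilities are Phi(c_j - mu) - Phi(c_(j-1) - mu). All 2 x 4 tables with 10 per group were enumerated. Each was weighted by its two multinomial probabilities, and power is the total weight of tables with p <= 0.05. Wilcoxon is the exact permutation test on mid-ranks.

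| Cut points | Where scores fall | Fisher % | Wilcoxon % | Gain |
|---|---|---|---|---|
| -0.15, 0.65, 1.45 | spread | 51.0 | 69.2 | 18.2 |
| 0.5, 1.2, 1.9 | spread, low-leaning | 49.4 | 65.3 | 15.9 |
| -0.8, 0, 0.8 | spread | 48.1 | 64.7 | 16.6 |
| -0.5, 0.65, 1.8 | spread, middle-leaning | 45.4 | 67.4 | 22.0 |
| quartiles of lower group | spread | 48.0 | 63.2 | 15.2 |
| -1, 0, 1 about the midpoint | spread | 47.8 | 68.6 | 20.8 |
| -1.5, 0.65, 2.8 | nearly all in 1+ and 2+ | 40.0 | 48.8 | 8.8 |
| 0, 0.3, 0.6 | mostly 0 or 3+ | 54.1 | 59.4 | 5.3 |
| -2, -1, 0.65 | mostly 2+ and 3+ | 42.2 | 50.7 | 8.5 |
| 1.5, 2.2, 3 | piled at 0 | 25.1 | 28.5 | 3.4 |

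In the last row the share at level 0 is Phi(1.5) = 93% in the lower group and Phi(1.5 - 1.3) = 58% in the higher.

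**Step 4: sensitivity.** A run over 13 cut-point sets, two of them in the table, gave Fisher 39-56% (10 of the 13 at 48-52%) and Wilcoxon 51-69%. If 1.3 SD is instead defined on the 0 to 3 score itself, Fisher gives 48-67% and Wilcoxon 69-74%. The rank test was ahead in every case run.

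**Step 5: type I error.** For the six spread sets with no shift, Fisher rejects in 2.6-4.3% and Wilcoxon in 2.2-4.0%. The gain is not bought with error.

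**Step 6: splitting the gap to 78.5%.** For the spread sets, Wilcoxon itself falls short by 78.5 - 69.2 = 9.3 to 78.5 - 63.2 = 15.3 points. That part comes from the four-level scale and the discreteness of exact tests. Ignoring order costs the further 15-22 points.

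**The case against.** The strongest reply is that the plan makes no power claim for this endpoint. A reader might infer from section 11.3, which mentions tumor tissue, that 80% is promised for endpoint 2b. The text does not support that. The figure is tied to a t-test, and tumor-tissue miR levels are analysed by t-test in section 11.2.2 item 4, so the mention of tissue has another referent. What stands is narrower: no power is given for endpoint 2b, and section 11.3 does not say so.

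A second reply is that the power figures rest on invented cut points. That is correct. They are conditional, and with concentrated scores the gain shrinks to 3-9 points. The direction of the difference did not change in any set examined.

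A third is that this is a descriptive pilot with no single primary efficacy analysis and no rule that turns a non-significant result into a conclusion of no HPV difference. A reader might fear that conclusion, but the plan does not prescribe it. The pre-treatment contrast is not a drug effect, and change is handled by another test. This limits the severity. It does not make an unordered test the better choice for an ordered score that section 11.1 lists as primary.

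Nor is the 0 to 3+ score clearly the only cellular measure in tumor. Section 8.3.4 also describes the percentage of tumor infiltrated and lymphocyte and macrophage scores from 0 to 300. If those were the analysed measure, the four-level calculation would not apply, but sections 11.1 and 11.2.2 specify 0 to 3+.

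**Conclusion.** The point holds as a minor, cheap improvement. It covers the two Fisher contrasts on endpoint 2b, pre- and post-treatment, and nothing else. Fisher's test is valid there but discards the order of the levels. On the latent-normal assumption with a 1.3 SD shift, it has about 45-51% power against about 63-69% for the exact rank test when patients are spread over the levels. Over more uneven cut points the figures are about 40-54% against 49-69%, a gain of 5-22 points. The gain is about 3 points, with both tests under 30%, when scores pile up at 0.

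A reader might go further and attribute the whole drop from 80% to Fisher, or expect a rank test to recover it. The calculation does not support either: 9-15 points of the shortfall remain under Wilcoxon even with well-spread scores.

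**What to change.** In section 11.2.2 item 3, replace Fisher's test with the exact (permutation, mid-rank) Wilcoxon-Mann-Whitney test for the pre- and post-treatment comparisons. Report P(HPV+ > HPV-) + 0.5 P(tie) with a 95% CI. The tie term is needed: with four equally likely levels and no difference, P(tie) = 4 x (1/4)^2 = 0.25, so P(HPV+ > HPV-) alone is (1 - 0.25)/2 = 0.375, which would look like an effect favouring HPV-. Adding 0.5 x 0.25 gives 0.5.

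Name one test. An exact linear trend test with scores 0 to 3 also uses the order but is not the same test: for the first four cut-point sets it has 61-65% power, against 65-69% for mid-rank Wilcoxon.

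In section 11.3 and the synopsis, state that 80% at 1.3 SD applies only to continuous measures analysed by t-test and that power for endpoint 2b is lower. Give any figure for endpoint 2b as a range with its assumed score distribution.

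The cost is wording, with no new data, visits or patients. The one loss is sensitivity to non-monotone differences, which no stated hypothesis predicts. The planned counts and percentages by group would still show them.
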